IRB00084686

NCT03042767

Anti-LPS Antibody in Pediatric Nonalcoholic Fatty Liver Disease

Short Name: Hyperimmune Milk in Pediatric NAFLD

Funding Source: National Institutes of Health & Immuron Ltd

Sponsor-Investigator:

Version Number: 5.0

IND Number: 17066

November 26, 2018

Anti-LPS Antibody in Pediatric Nonalcoholic Fatty Liver Disease

Short Name: Hyperimmune Milk in Pediatric NAFLD

Funding Source: National Institutes of Health & Immuron Ltd

Sponsor-Investigator:

Version Number: 5.0 IND Number: 17066

November 26, 2018

Responsible Persons and Institution

Principal Investigator: Name: Institution: Emory University School of Medicine

Research Pharmacist:

Contact person in case of serious adverse event:

Title:	Anti-LPS Antibody in Pediatric Nonalcoholic Fatty Liver Disease				
Version/Date:	Version 5 – April 3, 2017				
Study Phase:					
,					
Study Design: Indication:	12 week, randomized, double-blind, placebo-controlled, pilot study				
Number of Sites:	NAFLD				
	One, Emory University/Children's Healthcare of Atlanta				
Name of study drug:	IMM-124E				
Drug Dosage:	3 x 600 mg daily				
Route of administration:	Oral				
Conditions of administration:	Inclusion criteria: Age 6 – 19 years at time of initial screening NAFLD diagnosis (confirmed by biopsy, MRI, or Ultrasound) ALT ≥ 2 x ULN at screening (girls ≥ 46, boys ≥ 54) Written informed parent consent and child assent Willingness to consume IMM-24E 3 x daily for 12 weeks At least 2 months of attempted lifestyle changes after diagnosis Exclusion criteria: Disease or condition deemed by physician to interfere with absorption, digestion, or mechanism of intervention of drug Diagnosis of diabetes and an HbA1c of > 9% Change in supplement or anti-oxidant therapy within past 90 days (must be on a stable dose and willing to continue it throughout the trial or not on any vitamin or supplement, includes SAMe, vitatmin E, betaine, Milk thistle etc) Use of anti-NAFLD medications (metformin, thiazolidinediones, UDCA) in the 30 days prior to randomization Acute illness within past 2 weeks prior to enrollment (defined as fever > 100.4ºF) Planned pregnancy, nursing an infant, confirmed or suspected to be pregnant between screening and time of study enrollment Evidence of other chronic liver disease other than NAFLD (Hepatitis B and C, Alpha-1 antitrypsin, Wilson's disease) Intolerance to lactose or dairy-based products Unable to have blood drawn at study visits Unable to have blood drawn at study visits Current Gl bleeding or inflammatory bowel disease (IBD, colitis) <t< td=""></t<>				
	 Current enrollment in another therapeutic clinical that of receipt of an investigational study drug within 6 months prior to study enrollment Participants who are not able or willing to comply with the protocol or have any other condition that would impede compliance or hinder 				
	completion of the study, in the opinion of the investigator				
Number of participants:	40				

Primary Endpoints:	Percent change in ALT from Week 0 to Week 12 in treatment compared to placebo		
Secondary and	Mean change in ALT in treatment group compared to placebo		
Exploratory Endpoints:	Fasting glucose and insulin		
	Hemoglobin A1C		
	Adipo-IR		
	Oral glucose tolerance test		
	NAFLD pediatric diagnostic panel		
	Fasting plasma lipids		
	Stool microbiome		
	Blood transcriptomics		
	Systemic inflammation (cytokines)		
	Metabolomics		
	Visceral Adiposity (AMRA MRI scan)		
	Hepatic fat percent (AMRA MRI scan)		
	BMI z-score		
	Waist circumference		
	Depression		
	Quality of life		
	 Composite endpoint of "metabolic improvement" specified as >10% 		
	improvement in TG/HDL ratio, improvement in insulin resistance, and >10%		
	improvement in ALT		
Study Duration (per	Up to 19 weeks total		
participant):	• Up to 6 weeks screening		
	12 week treatment		
Study Duration (calendar	• Study start-up: 0 – 4 months		
time):	Recruitment phase: 5 -14 months		
	Follow-up phase: 15 - 18 months		
Math Cale a duile :	Analysis and reporting: 18 - 24 months		
Visit Schedule:	Screening Visit		
	Baseline visit		
	Follow up visits		
Ctatistical Analysis	• Week 6 and Week 12 visits		
Statistical Analysis:	Descriptive variables of the cohort and subgroups will be analyzed using means and standard deviations or medians and ranges, as appropriate. Percent change in		
	primary and secondary outcomes will be compared using two sample t-test or		
	Mann-Whitney test. Absolute change over time will be compared using mixed		
	model or analysis of covariance.		
Sample Size:	A sample size of 11 participant per group is required to achieve a least 90% power		
Sample Size.	to detect a 15% point difference in the average % change in ALT from baseline to		
	week 12 between the two groups. Sample size was calculated assuming common		
	standard deviation of 10% using a two-sided Mann-Whitney tests with a 0.05		
	significance level. We will include 20 participants per group to allow for drop out,		
	intra-individual variability and multiple hypothesis testing.		
Safety Monitoring:	A DSMB will monitor the data for safety and efficacy for outcomes such as nausea,		
earcey monitoring.	abdominal pain, flatus, diarrhea, pregnancy, hepatotoxicity and any other outcomes		
	or events identified as safety related.		

Table of Contents

1.1 Primary Objectives71.2 Secondary Objectives72. Background & Significance73. Study Design113.1 Design Overview113.2 Inclusion Criteria113.3 Exclusion Criteria113.4 Rescreening123.5 Treatment Groups123.6 IMM-124E Administration123.7 Recruitment and Retention133.8 Sources and Materials133.9 Potential Risks133.10 Protection Against Risks143.11 Potential Benefits153.12 Data and Safety Monitoring164. Study Plan16
2. Background & Significance.73. Study Design.113.1 Design Overview.113.2 Inclusion Criteria.113.3 Exclusion Criteria.113.4 Rescreening.123.5 Treatment Groups.123.6 IMM-124E Administration.123.7 Recruitment and Retention.133.8 Sources and Materials.133.9 Potential Risks.133.10 Protection Against Risks.143.11 Potential Benefits.153.12 Data and Safety Monitoring.16

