5.2 Secondary Endpoints

Secondary efficacy-related outcomes will include change in: GGT, fasting glucose and insulin, total body insulin sensitivity (OGTT), BMI z-score, waist circumference, and quality of life. Safety-related outcomes will include: sex hormones, proportion of participants with nausea, emesis, diarrhea, and any other adverse event, PROMIS, body fat by MRI, hepatic fat by MRI, and change in metabolic state.

5.3 Power Analysis:

A typical group of patients with NAFLD have a mean ALT level of $130 \pm 63 \text{ U/L}^{10}$. In the TONIC treatment study of children with NAFLD, there was a -20 ± 10 U/L and -30 ± 8 U/L change (average of 15% – 23% change) in ALT in treatment groups respectively and no change in ALT with placebo at 12 weeks⁶. A sample size of 11 participant per group is required to achieve a least 90% power to detect a 15% point difference in the average % change in ALT from baseline to week 12 between the two groups. Sample size was calculated assuming common standard deviation of 10% using a two-sided Mann-Whitney tests with a 0.05 significance level.

5.4 Statistical Analysis:

Primary Outcome Analysis:

Change in ALT from baseline to week 12 will be converted to a % change from baseline to account for the wide range of ALT values expected at baseline. A Mann-Whitney U test will be used to compare the percentage change in ALT among the two intervention groups. Data will be described as mean or median percent change, as appropriate.

General Statistical Considerations:

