Analysis of primary and secondary outcomes will be performed using an intention to treat analysis. Descriptive variables of the cohort and subgroups will be analyzed using means and standard deviations, medians and ranges, or counts and percentages, as appropriate. For secondary measures, absolute change over time will be compared using mixed models or analysis of covariance. We will test the data to evaluate underlying model assumptions (i.e., normality, homoscedasticity). If these assumptions are not met, then we will attempt to transform the data. Standard transformations of the response variable such as the log, square root and Box-Cox transformations will be examined. If data transformation is inadequate to meet the analysis assumptions, then rank transformation of the data will be performed and the rank transformed response variables will be analyzed and reported. In situations where covariates could potentially have an effect on the response variable, we will add covariates to adjust for subgroup effects. Underlying model assumptions will be tested (such as homogeneity of slopes across exposure groups). Standard regression criteria will be used to assess appropriateness of including particular covariates. Collinearities will be reduced in multivariable modeling through the careful initial assessment of correlations and the avoidance of redundancies in candidate covariates.

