With multiple follow-ups, longitudinal data will be available, and these repeated measures are likely to be correlated (i.e., weight, PROMIS measures, BMI-score, etc.). The analysis of repeated measures data is needed that properly accounts for the correlation between multiple observations from the same participant. Mixed effects models, accounting for the longitudinal measures, will be summarized with adjusted means and 95% confidence intervals for continuous outcomes. For categorical outcomes, we will apply generalized linear mixed models with appropriate distribution and link functions. In these models, the statistical test for interaction between time on study and intervention group will be the primary overall hypothesis to test to determine whether an outcomes in the two study groups changed in significantly different ways during follow-up (i.e., different temporal patterns over time). For significant interactions, post-hoc tests will be used to compare differences in the least square means at each time point in each intervention arm. All statistical tests will be two-sided and unadjusted for multiple comparisons due to the pilot nature of this trial.

Missing Data: A potential problem in any of the proposed analyses is missing data, which can cause the usual statistical analysis of complete available data to be subject to bias. Every effort will be made to minimize missing data on outcomes and covariates, and we will encourage patients that drop out of a study to return for final follow-up testing even if they missed previous scheduled evaluations.

Sensitivity Analysis: A sensitivity analysis will be performed by examining the effect of compliance (i.e., number of doses taken) on the primary and secondary endpoints.

5.5 Data Storage & Sharing:

Hard copy data will be entered by the study coordinators. All data will be stored in a REDCap database. Only study personnel (PI, Co-I's study coordinators, research assistants etc.) will have access to identifiable data. Data will be de-identified before analysis. Data will be stored in locked research material cabinets and in password-secured on the Emory network.

De-identified data will be shared with Immuron Ltd. and a sub-set of de-identified data will further be shared with Advanced MR Analytics AB (AMRA) who is providing imaging analysis services for the study.

5.6. Sample storage:

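### For continuous secondary outcomes the synopsis plans both percent change and absolute change, section 5.4 plans only absolute change, nothing says which scale decides, and percent change is not valid for BMI z-score

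*Combined protocol and SAP*

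**What the plan says.** **Synopsis, Statistical Analysis.** The sentence takes percent change as its subject and continues: "primary and secondary outcomes will be compared using two sample t-test or" Mann-Whitney. The text then runs on: "Mann-Whitney test. Absolute change over time will be compared using mixed" model or ANCOVA. The second sentence does not name its outcomes, so both scales are open for secondary outcomes.

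**Section 5.4, Primary Outcome Analysis.** Change in ALT is "converted to a % change from baseline to account for the wide range of ALT values expected at baseline", and "A Mann-Whitney U test will be used to compare the percentage change in ALT among the two intervention groups". Both the scale and the reason for it are given for ALT alone.

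**Section 5.4, General Statistical Considerations.** "For secondary measures, absolute change over time will be compared using mixed models or analysis of covariance". In the repeated-measures models, "the statistical test for interaction between time on study and intervention group will be the primary overall hypothesis to test". Tests are two-sided and carry no multiplicity adjustment, which the plan justifies by the pilot nature of the trial.

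**Section 5.2.** The secondary efficacy outcomes are listed as changes, including "total body insulin sensitivity (OGTT), BMI z-score, waist circumference, and quality of life", with no statement of percent or absolute.

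**Section 5.1.** If ALT misses but important secondary markers succeed, the plan will take that as support for designing further studies.

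**The concern.** A continuous secondary outcome such as fasting insulin, hepatic fat percent or BMI z-score can be analysed on two scales, and the plan does not rank them. The scales answer different questions. A fall in hepatic fat from 20% to 15% is -25% on one and -5 points on the other.

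Two things are at stake. First, section 5.1 lets secondary results carry weight if ALT fails, so a choice of scale made after seeing the data could affect what is taken forward. Declaring no adjustment across endpoints does not cover choosing between two analyses of the same endpoint. Second, for BMI z-score one of the two stated analyses is not meaningful, whatever the data show.

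**Working it through.** **1. The plan's own figure.** The only design calculation is for the primary outcome: a 15-point difference, SD 10 points, two-sided 0.05, 90% power, 11 per group (section 5.3).
- Normal approximation: n = 2 × (1.960 + 1.282)² × 10² / 15² = 9.3, so 10 per group.
- Noncentral t power is 88.7% at 10 and 91.7% at 11. With the Mann-Whitney efficiency of 0.955 it is 90.3% at 11. Simulated Mann-Whitney power at 11 is about 90%.

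The stated 11 is reproduced. It concerns percent change in ALT, which both places define in the same way, so this point does not touch it.

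**2. The two places side by side.**

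| | Percent change | Absolute change |
|---|---|---|
| Synopsis | primary and secondary; t-test or Mann-Whitney | outcomes not named; mixed model or ANCOVA |
| Section 5.4 | ALT only; Mann-Whitney | secondary measures; mixed model or ANCOVA |

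The absolute-change column agrees. The discrepancy is an extra percent-change analysis of secondary outcomes in the synopsis, with no order of priority.

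**3. BMI z-score.** Percent change = 100 × change / baseline. The baseline values here are illustrative.
- A shift of 0.2: 0.2/2.4 = 8%; 0.2/0.2 = 100%.
- A change of -0.1: -20%, -10%, -5% and -4% at baselines 0.5, 1.0, 2.0 and 2.5; at baseline -0.2 it is +50%, so an improvement is scored as a worsening.

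Section 3.2 sets no minimum BMI, so small baselines are not excluded. The documents do not show how common they would be.

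**4. Null rejection rate with both scales available.** Simulation with 20 per arm (synopsis) and each test at two-sided 0.05. The documents give no spreads for these outcomes, so all spreads are assumptions. Skewed positive outcomes are lognormal with CV 0.4-0.7 and baseline-to-Week-12 correlation 0.6-0.8. BMI z-score is normal with baseline mean (SD) 2.2 (0.4), 1.8 (0.6) or 1.5 (0.7) and SD of change 0.15. ANCOVA regresses change on baseline and arm; using the Week 12 value instead gives the same arm effect.

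| No true effect | Skewed outcome | BMI z-score |
|---|---|---|
| Either test alone | about 5% | about 5% |
| Mann-Whitney on % change, or ANCOVA | 7.3-7.8% | 6.3-6.8% |
| Adding the t-test on % change | 8.0-8.9% | 6.8-7.6% |

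A separate simulation with one assumed setting per type gave 7.0% and 6.2% for the two-test rule, and 7.9% and 6.8% for three. Two independent tests would give 1 - 0.95² = 9.75%.

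**5. Disagreement with a true 25% reduction.** Over the same skewed settings, percent-change Mann-Whitney and absolute-change ANCOVA fall on different sides of 0.05 in 4-21% of trials.

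**6. Power for BMI z-score.** The assumed effect is -0.15. By hand, effect/SD = 1, noncentrality = √(20/2) = 3.16, and approximate power = Φ(3.16 - 1.96) = 88%, slightly less with t critical values.

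| Baseline mean (SD) | ANCOVA | % change, Mann-Whitney | % change, t-test |
|---|---|---|---|
| 2.2 (0.4) | 86-87% | 84% | 86% |
| 1.8 (0.6) | 86-87% | 81% | 71% |
| 1.5 (0.7) | 86-87% | 75% | 43% |

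The cause is the denominator. In the last row a baseline two SDs below the mean is 1.5 - 1.4 = 0.1, where -0.15 counts as -150%. At the mean it counts as -10%. A few such participants dominate the t-test.

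**The case against.** - **The two places do not flatly conflict.** A reader might infer a percent-change synopsis set against an absolute-change section 5.4. The documents do not support that: the synopsis also plans absolute change, and section 5.4 is silent on percent change for secondary measures rather than ruling it out. This stands, and it leaves an extra analysis with no stated priority.
- **Not every secondary endpoint is affected.** Mean change in ALT is named with its own scale, the metabolic composite is a responder definition, categorical outcomes have generalized linear mixed models, and percent change has no clear meaning for the stool microbiome or transcriptomics. This stands; the point is limited to continuous secondary outcomes.
- **The disagreement is about p-values near 0.05.** A reader might infer opposite conclusions. In a repeat simulation no trial had both tests significant in opposite directions. Choices within one scale also disagree: t-test against Mann-Whitney on percent change in 2-11% of the skewed trials, raw against log ANCOVA in 3-18%. This stands.
- **The inflation is modest and not unique to this discrepancy.** Section 5.4 itself allows raw, log or rank analysis after assumption checks, and picking among those gave 6.9-7.8% under the null. A 0.05 level is stated only for the primary calculation, and the pilot openly makes no adjustment. This stands, and it means that deleting words in the synopsis would not by itself remove the choice.
- **The BMI z-score power loss depends on assumed baselines.** At 2.2 (0.4) it is at most about 3 points, and Mann-Whitney keeps at least 75% in all three settings. This is true of the power figures. The arbitrary zero and the sign reversal need no simulation.

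**Conclusion.** The point holds for continuous secondary outcomes. The synopsis offers two scales, section 5.4 one, and neither says which is decisive. For BMI z-score the percent-change rule is wrong whatever the data.

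The effect is modest: null rejection of about 7-8% per endpoint instead of 5% (6-7% for BMI z-score), and disagreement on significance in about 4-21% of trials with a true 25% reduction. The percent-change t-test for BMI z-score loses power as baselines approach zero. These sizes rest on 20 per arm and on assumed spreads, correlations and baselines. The wording discrepancy and the BMI z-score arithmetic do not.

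A reader might also infer that the trial's main result is at risk. It is not: the scale of the primary outcome is settled and its sample size reproduces. The correction is minor to moderate in weight, and worth making because secondary findings may guide later studies.

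**What to change.** 1. In the synopsis, delete *and secondary*, so that percent change applies to the primary ALT outcome only.
2. State in both places that continuous secondary outcomes are judged by the baseline-adjusted section 5.4 model. Where Week 6 data exist (for example BMI z-score and waist), use the mixed model with its time-by-group test. Where only Weeks 0 and 12 exist (for example MRI, OGTT and PROMIS), use ANCOVA on the baseline value. Replacing all of these with a Week 12 ANCOVA would discard Week 6 and displace the interaction test that section 5.4 already names.
3. Name the log scale in advance for strictly positive, skewed laboratory values such as insulin, triglycerides and GGT, back-transformed to a percent difference between arms. This keeps a relative reading and narrows the choice of transformation left open in section 5.4. In the skewed settings above, power for the 25% reduction was 97%, 75%, 41% and 63% with log ANCOVA, against 95%, 67%, 33% and 57% with percent-change Mann-Whitney.
4. Treat any percent-change summary of a secondary outcome as descriptive, and compute none for BMI z-score.

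The cost is a few sentences of wording, with no new data or participants. The sponsor gives up an alternative p-value for each continuous secondary outcome.

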7.1 Study Schedule of Events	
7.2 Blood Collection Schedule	

1. Objectives

We hypothesize that IMM-124E, a bovine colostrum enriched with anti-LPS antibodies, will improve insulin resistance and decrease systemic and hepatic inflammation through modulation of bacterial products and the microbiome in pediatric NAFLD.

1.1 Primary Objective: The principal objective of this blinded, placebo-controlled, pilot study is to evaluate whether 12 weeks of IMM-124E in children with NAFLD in combination with standard of care (SOC) will decrease inflammation in the liver as measured by ALT. Specifically, percent change in ALT from Week 0 to Week 12 in treatment compared to placebo.

1.2 Secondary Objectives:

- To assess the safety and tolerability of IMM-124E in children with NAFLD
- To assess the effects of IMM-124E on secondary and exploratory endpoints:
 - Mean change in ALT in treatment group compared to placebo
 - Fasting glucose and insulin
 - Hemoglobin A1C
 - o Adipo-IR
 - Oral glucose tolerance test
 - NAFLD pediatric diagnostic panel
 - Fasting plasma lipids
 - Stool microbiome
 - Blood transcriptomics
 - Systemic inflammation (cytokines)
 - Metabolomics
 - Visceral Adiposity (AMRA MRI scan)
 - Hepatic fat percent (AMRA MRI scan)
 - o BMI z-score
 - Waist circumference
 - Depression
 - Quality of life
 - Composite endpoint of "metabolic improvement" specified as > 10% improvement in TG/HDL ratio, improvement in insulin resistance, and >10% improvement in ALT

2. Background and Significance

Nonalcoholic fatty liver disease (NAFLD) is an aggressive, obesity-associated chronic liver disease that affects ~7 million children in the US (10% of all children) and is one of the top 3 indications for liver transplant in adults. Currently, the only treatment available for NAFLD is lifestyle advice to decrease adiposity and improve insulin sensitivity but this is rarely effective. It is our long term goal to improve the health of children by understanding how to prevent, treat and cure NAFLD. In our previous studies, we demonstrated that children with NAFLD have endotoxemia as well as systemic inflammation. Further, individuals with NAFLD have a disturbed microbiome (dysbiosis) and increased gut permeability. Thus, the mechanism of NAFLD is thought to include chronic inflammation from intestinal microbiome-derived

products (lipopolysaccharide (LPS) and metabolites) which pass through the "leaky gut" to the liver where they activate the innate immune response.

IMM-124E is a hyperimmune colostrum-derived product from cows inoculated with bacterial products from 13 strains of *E. coli*. Preliminary data suggests that IMM-124E improves insulin sensitivity, reduces liver inflammation and promotes regulatory T cells that suppress chronic inflammation. IMM-124E acts at the level of the mucosa in the gut by improving barrier function and decreasing systemic exposure to microbial products (LPS). It could also alter the gut microbial populations by targeting pathogenic bacteria (*E. coli*). IMM-124E is being tested in adults for treatment of NAFLD and alcoholic hepatitis under 2 separate FDA approved INDs. A similar product is sold over-the-counter in Canada and Australia. IMM-124E is considered a medical food and *little is known regarding its potential use in children*. It is important to study in children because the NAFLD histology is different compared to adults. Waiting for the results of adult trials will have little benefit for children. The objective of this proposal is to evaluate the preliminary effectiveness, safety and mechanisms of action of IMM-124E in children with NAFLD.

In this proposal, we will test the following central hypothesis: IMM-124E, a bovine colostrum enriched with anti-LPS antibodies, will improve insulin resistance and decrease systemic and hepatic inflammation through modulation of bacterial products and the microbiome in pediatric NAFLD. The aims of this study are the following:

- To determine if a 3-month treatment with IMM-124E in combination with standard of care lifestyle advice (SOC) is safe and results in greater improvement in 1) hepatic inflammation (alanine amino transferase - ALT) 2) insulin sensitivity 3) blood lipids in children with NAFLD compared to placebo with SOC as well as safety related endpoints.
- 2. To define mechanism of action related endpoints in response to 3 months of IMM-124E in children with reduction in the above outcomes including: stool microbiome (16S rRNA), metabolomics, intestinal inflammation (stool calprotectin), systemic inflammation (cytokines), transcriptomics (immune response) and correlate these with changes in clinical measurements.

We will test our hypothesis and accomplish the aims through a randomized, double-blind, 3 month treatment trial of children age 6-19 years with a diagnosis of NAFLD by biopsy or MRI. IMM-124E and placebo will be provided by Immuron. Patients will be recruited from the Children's Healthcare of Atlanta pediatric liver clinical practice which cares for over 400 pediatric NAFLD patients and has an extensive record of successful clinical trials in children. The sample size of 40 participants is powered for change in ALT as the primary outcome and allows sufficient power for subgroup analysis and secondary outcomes. High resolution, high throughput metabolomics will be combined with transcriptomics of PBMCs, 16S rRNA characterization of the stool microbiome to determine gut-level and system-level response to IMM-124E.

These studies are designed to inform decision making about the design of a future large, multicenter trial testing IMM-124E. We will leverage our position as members of the NIH supported clinical research network (NASH CRN) in which pediatric investigators are eager to conduct a phase III trial of IMM-124E if

the data shows promise. These studies have great potential to advance progress towards a new therapeutic for NAFLD, thus improving health for millions of children.

Why study pediatric NAFLD? NAFLD is a chronic liver disease defined by accumulation of fat in the liver in the absence of alcohol or other secondary causes of steatosis¹. In the US, over 7 million children are estimated to have it². NAFLD occurs in the setting of insulin resistance (IR) and it is histologically categorized into nonalcoholic fatty liver (NAFL), a milder form without hepatocellular injury and nonalcoholic steatohepatitis (NASH), defined as hepatic fat plus hepatocellular injury with or without fibrosis¹. In children, NAFLD often presents as NASH with fibrosis at diagnosis^{3, 4}. It is crucial to study pediatric NAFLD in children because it is commonly severe and there is not yet an effective treatment for it. Further, pediatric NAFLD differs from adult NAFLD because in children the histology frequently has zone 1 accentuation (portal based) chronic inflammation and fibrosis as opposed to zone 3 (central venule), which is classic in adults. Zone 1 predominance of inflammation suggests that toxins are delivered by the portal venous blood from the gut to the liver. Previous therapeutics for NAFLD have included antioxidants (vitamin E) and metformin; however neither sufficiently improved histopathology^{5, 6}. Finding a treatment for NAFLD will prove most beneficial to children by avoiding a lifetime of increased risk of cirrhosis, cardiovascular disease and type II diabetes.

Why target the gut to treat NAFLD? The cause of NAFLD is multifactorial, resulting from a combination of genetic suceptibility and environmental hits modified by individual factors such as the microbiome. Among Hispanic children, the rs738409 polymorphism of PNPLA3 is associated with increased hepatic fat in children as young as 8-10 years of age⁷ only in the setting of a high sugar diet⁸, suggesting a strong geneenvironment interaction. Our group previously showed that children with NAFLD are less tolerant to fructose and have increased post prandial hypertriglyceridemia compared to those without⁹. Further, we studied the response to diet in these same

children and found that endotoxin levels rise immediately postprandially in NAFLD while in obese and normal weight children they do not¹⁰. Increased endotoxin results from a combination of altered microbiota composition (dysbiosis) and increased gut permeability from disruption of tight junctions, thus allowing increased movement of microbial products from the lumen into the portal blood stream into the liver (reviewed in¹¹ Figure 1). Supporting this, pediatric NAFLD studies have shown increased Gammaproteobacteria and *Prevotella* as well as increased energy production by the microbiota¹². There is growing consensus that treatment for NAFLD at the intraluminal level is needed¹²⁻¹⁶.

Why use IMM-124E to treat pediatric NAFLD? In a mouse model of extreme obesity, treatment with anti-LPS enhanced bovine colostrum (similar to IMM-124E) led to decreases in IR, alanine amino transferase (ALT) levels and serum triglycerides when compared to control mice, and decreases in serum TNFα levels¹⁹. IMM-124E was used to treat 10 adults with biopsy-proven NASH for 30 days in an open-label pilot study¹⁸. IR improved in all participants and an improved lipid profile and liver enzymes was seen in 5 out of 10. There are two active trials using IMM-124E reported on clinicaltrials.gov. One is a 30 day RCT treating patients with alcoholic hepatitis sponsored by the NIH and the other is an industry sponsored phase II study of IMM-124E for patients with NASH. Bovine colostrum has been well-tolerated in previous studies. The most common adverse events are nausea, abdominal pain, flatus and/or diarrhea and all are rare.

What is known about the mechanisms of IMM-124E in NAFLD and what needs to be tested? IMM-124E acts through targeting bacterial products (LPS) at the mucosal surface, before transference into the portal blood. LPS is thought to activate TLR signaling which then induces upregulation of inflammatory pathways such as activation of NF κ B pathway and subsequent altered expression of adipocytokines known to be important in NAFLD including tumor necrosis factor alpha (TNF α) and interleukin-6. In animal models, LPS has been shown to induce hepatic steatosis as well as hepatic inflammation and fibrosis progression²⁰. In adults with NAFLD, several studies show elevated LPS²¹ or anti-LPS antibodies²², while NAFLD treatment is associated with improvement in LPS levels and liver enzymes²³ after 6 months. Thus, the theoretical basis for utilization of IMM-124E as a therapy of NAFLD in children is that IMM-124E taken 3 x daily will block LPS in the gut, decreasing the transfer of LPS to the liver and plasma, thus alleviating chronic inflammation, improving insulin sensitivity and leading to decreased inflammation.

In summary, pediatric NAFLD affects many children and is often severe. The pathophysiology of NAFLD involves increased microbial products (LPS) entering the liver through the portal blood causing chronic inflammation. There is no effective treatment available yet. IMM-124E is a medical food approved for over-the-counter sales in the US and may decrease endotoxin in the setting of NAFLD. It has not yet been tested in children and preliminary data is needed. It is thought to be highly safe; although further confirmation of this is prudent. Thus, exploratory studies of IMM-124E in pediatric NAFLD are needed.

3. Study Design

3.1 Design Overview:

This is a 12 week randomized, double-blind, placebo-controlled "proof of concept" trial (RCT) testing the effect of IMM-124E on change in ALT in children with NAFLD. A placebo-controlled trial was selected because this is the highest quality method and pediatric NAFLD has a substantial placebo response rate (typically ranges from no change to a 30 U/L improvement in ALT at 12 weeks after the initial diagnosis by liver biopsy). Further, a parallel arm trial is necessary because the sustainability of IMM-124E influence is not known and thus the appropriate length of a wash-out period was unclear. ALT is an accepted surrogate marker of hepatic inflammation in children and improvements can be seen within several weeks in pediatric NAFLD⁶.

3.2 Inclusion criteria:

- Age 6 19 years at time of initial screening
- NAFLD diagnosis (confirmed by liver biopsy, MRI, or Ultrasound)
- ALT $\ge 2 \times ULN$ at screening (girls ≥ 46 , boys ≥ 54)
- Written informed parent consent and child assent
- Willingness to consume the investigational product 3 x daily for 12 weeks
- At least 2 months of attempted lifestyle changes after diagnosis

3.3 Exclusion criteria:

- Disease or condition deemed by physician to interfere with absorption, digestion, or mechanism of intervention of drug
- Diagnosis of diabetes and an HbA1c of > 9%
- Change in supplement or anti-oxidant therapy within past 90 days (must be on a stable dose and willing to continue it throughout the trial or not on any vitamin or supplement, includes SAMe, vitamin E, betaine, Milk thistle etc)
- Use of probiotics or antibiotics in the past 30 days
- Use of anti-NAFLD medications (metformin, thiazolidinediones, UDCA) in the 30 days prior to randomization
- Acute illness within past 2 weeks prior to enrollment (defined as fever > 100.4ºF)
- Planned pregnancy, nursing an infant, confirmed or suspected to be pregnant between screening and time of study enrollment
- Evidence of other chronic liver disease other than NAFLD (Hepatitis B and C, Alpha-1 antitrypsin, Wilson's disease)
- Intolerance to lactose or dairy-based products
- Unable to have blood drawn at study visits
- Unwillingness to provide and/or collect stool samples
- Current GI bleeding or inflammatory bowel disease (IBD, colitis)
- Current enrollment in another therapeutic clinical trial or receipt of an investigational study drug within 6 months prior to study enrollment
- Participants who are not able or willing to comply with the protocol or have any other condition that would impede compliance or hinder completion of the study, in the opinion of the investigator

